# 7.6.2. Blinding

Oxytocin and placebo bottles will be identically matched in appearance and the bottle labels will not reveal the drug identity. The site investigator or designated approved study physician will make the decision to un-blind the identity of the investigational product in the event that the study blind needs to be broken to make medical decisions regarding subject treatment. If it is determined that unblinding is necessary to assess AEs or SAEs for expedited reporting, NIAAA may decide to request unblinding of a subject. Site staff or Sponsor's designee approved to un-blind the study drug will log into the IWRS to obtain the name of the investigational product to which the subject was randomized. The IWRS will automatically notify the un-blinded staff member at the Data Coordinating Center who will notify the Medical Monitor. NIAAA will be notified that an unblinding has occurred if unblinding has been performed by the investigator or medical monitor. Prior experience with oxytocin nasal spray compared with placebo nasal spray has not indicated that any differences would be noticed between formulations.

# 7.7. Interventions on Day 1

At study Day 1, after the subject is randomized, he/she will receive the first vial of intranasal investigational product, and an instruction sheet. The vial(s) being dispensed will be weighed prior to providing it to the subject. Site staff will explain the dosing plan to the subject and how to complete a Diary Card to track when doses are taken. The subject will administer the first dose while in the clinic on Day 1 under observation by site staff to make sure that the subject is using the nasal spray appropriately. The subject will watch the first module of Take Control, will be given the schedule of visits, and the Week 2 visit will be scheduled.

Every study subject will be provided with a wallet card and instructed to carry this card that identifies the potential investigational products that s/he could be taking during the study. The card will provide the name and 24-hour phone number of the investigator (physician) at the site who can be contacted in the event of an emergency. The card will also instruct the non-study physician rendering emergency care to contact the study physician and inform him/her about the care. Prior to release from the clinic, the subject will be asked if they are experiencing any side effects from the first dose of investigational product.

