3.2 Study Design

This study is a double-blind, randomized, placebo-controlled, parallel group, multi-site clinical trial designed to assess the efficacy of oxytocin compared with placebo to reduce drinking in 100 subjects (50 in each group) who report 4 or more Diagnostic and Statistical Manual of Mental Disorders – Fifth Edition (DSM-5TM) symptoms of AUD. This study will be conducted at 4 clinical sites. If eligible for the study, subjects will be randomized using a stratified permuted block randomization procedure with "clinical site" as a stratification variable in an approximate 1:1 ratio (targeting 50 subjects per group) to receive either intranasal oxytocin or placebo for 12 weeks.

[figure not shown]
If eligible for the study, subjects will receive blinded intranasal oxytocin at 35 IU once per day or intranasal placebo (same volume once per day) for 2 weeks (initial tolerability assessment period), then for the next 10 weeks (maintenance period) subjects will receive oxytocin at 35 IU/twice per day (BID, totally daily dose 70 IU) or intranasal placebo (same volume twice per day)

Subjects will be seen in the clinic at screening visit(s), at randomization, and at Weeks 2, 3, 4, 6, 8, 10, and 13. During the alternate weeks when subjects will not be coming into the clinic (Weeks 5, 7, 9, 11, and 12), subjects will be contacted once during that week by telephone to encourage study drug compliance and to assess withdrawal, adverse events (AEs), and concomitant medication use. A final follow-up telephone interview will occur during Weeks 14/15 (1-to-2 weeks after the end of dosing).

Enrollment will be halted if 2 or more at least possibly related SAEs as judged by the investigator or medical monitor occur. If this occurs, a DSMB meeting will be convened and a decision, in conjunction with the study Sponsor, will be made regarding stopping the study.

The overall study schema is provided in Figure 1. The study schedule of visits and assessments is shown in Table 1.

Figure 1. Overview of Study Design

*Telephone contact, otherwise visit is in clinic

Oxytocin for Alcohol Use Disorder Protocol Number: NCIG-007R

Table 1. Schedule of Assessments

	Screen						ľ	Mainte	nance					EOS ^a	Safety Follow-up
Study Week	-2 to -1	1	2	3	4	5	6	7	8	9	10	11	12	13	14/15
Clinic Visit #	1	2	3	4	5		6		7		8			9	
Informed Consent	X														
Alcohol Breathalyzer	X	X	X	X	X		X		X		X			X	
Urine Drug Screen ^b	X	X	X	X	X		X		X		X			X	
Locator Form	X														

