7.0 SAMPLE SIZE CONSIDERATIONS

With an intake sample of 100 subjects (50 subjects per arm) and 12% attrition, it is projected that the sample size for primary endpoint analyses will be 88 (44 subjects per arm). The alpha level for the primary analyses will be 0.05, two-tailed. An estimate of the effect size (Cohen's d) for the investigational products is 0.60. Equal variances in both groups are assumed. These assumptions lead to a projected power of 0.80.

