9.0 STATISTICAL CONSIDERATIONS

9.1 General Considerations

For descriptive purposes, dichotomous and categorical variables will be presented as number of observations and percentages; continuous variables will be given as means, standard deviations (SD), median, minimum (min) and maximum (max). Statistical tests will be two-tailed at a 0.05 Type I error rate. P-values for the primary and secondary endpoints of < 0.05 will be considered statistically significant. Endpoint data will also be screened for outliers and skewness. Appropriate non-parametric tests will be used to compare treatment groups on continuous baseline characteristics that are not normally distributed. Continuous endpoint data that are not normally distributed will be transformed using either a square root, logarithmic, or inverse transformation, the selection of which is determined by skewness and kurtosis statistics with values closest to zero and normalization of histograms. Cohen's d will be used to calculate the effect size for means. Odds ratios will be provided for all dichotomous outcomes. Descriptive statistics – mean, SD, median, min and max – of all endpoint data will be provided for each assessment point or summarized at each week for drinking endpoints. All data will be presented in listings. All analyses will be performed in the full analysis set.

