Week 3 (xx) Week 12 (xx)	XX	XX.X	XX.X	XX.X	XX.X	XX.X	XX	XX.X	XX.X	XX.X	XX.X	XX.X	0.xxx
Overall (Weeks 1-12)													
Total number of insufflations	XX	XX.X	XX.X	XX.X	XX.X	XX.X	XX	XX.X	XX.X	XX.X	XX.X	XX.X	0.xxx
Total number of insufflations	XX		XX.X	XX.X	XX.X	XX.X			XX.X	XX.X	XX.X	XX.X	0.xxx
Weeks 1-2		XX.X					XX	XX.X					
Total number of insufflations	XX		XX.X	XX.X	XX.X	XX.X			XX.X	XX.X	XX.X	XX.X	0.xxx
Weeks 3-12		XX.X					XX	XX.X					
¹ p-value from t-test for continuous	variables	s (t) – skev	ved cont	inuous c	lata uses	the Wilc	oxon rai	nk-sum tes	t (w).				
² Number of insufflations per week													
³ xx maximum number.possibible in	week												

Table 4: Percent Compliance to Investigational Products Based on Subject Diary

			Plac	ebo					Oxyt	ocin			
Period	n	Mean	SD	Med	Min	Max	n	Mean	SD	Med	Min	Max	p-value ¹
Insufflations ²													
Week 1	XX	XX.X	XX.X	XX.X	XX.X	XX.X	XX	XX.X	XX.X	XX.X	XX.X	XX.X	0.xxx
Week 2	XX	XX.X	XX.X	XX.X	XX.X	XX.X	XX	XX.X	XX.X	XX.X	XX.X	XX.X	0.xxx
Week 3 Week 12	XX	XX.X	XX.X	XX.X	XX.X	XX.X	XX	XX.X	XX.X	XX.X	XX.X	XX.X	0.xxx
Overall (Weeks 1-12)													
Total number of insufflations	XX	XX.X	XX.X	XX.X	XX.X	XX.X	XX	XX.X	XX.X	XX.X	XX.X	XX.X	0.xxx
Total number of insufflations	XX		XX.X	XX.X	XX.X	XX.X			XX.X	XX.X	XX.X	XX.X	0.xxx
Weeks 1-2		XX.X					XX	XX.X					
Total number of insufflations	XX		XX.X	XX.X	XX.X	XX.X			XX.X	XX.X	XX.X	XX.X	0.xxx
Weeks 3-12		XX.X					XX	XX.X					

¹ p-value from t-test for continuous variables (t) – skewed continuous data uses the Wilcoxon rank-sum test (w).
² percent is the # of sprays taken/#of sprays presecribed in a period

Table 5: **Exposure to Investigational Products Based on Weight of Vials**

Note that this is the same as Table 2 except using IU for dosing

Table 6: Percent Compliance to Investigational Products Based on Weight of Vials

Note that this is the same as Table 3 except using IU for dosing and percent is based upon IU taken/IU presecribed

Table 7: Summary of Medical History

MedDRA SOC/	Placebo	Oxytocin
Preferred Term	(N=xx)	(N=xx)
SOC	nn (xx.x%)	nn (xx.x%)
- Overall -		
Preferred term 1	nn (xx.x%)	nn (xx.x%)
Preferred term 2	nn (xx.x%)	nn (xx.x%)

Table 8: Exit Interview

	Placebo	Oxytocin	Total	
Question	(N=xx)	(N=xx)	(N=xxx)	p-value ¹
What medication do you believe you were taking?				0.xxx
Placebo	xx (xx.x%)	xx (xx.x%)	xx (xx.x%)	O.MM
Active	xx (xx.x%)	xx (xx.x%)	xx (xx.x%)	
Both Active & Placebo	xx (xx.x%)	xx (xx.x%)	xx (xx.x%)	

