No Idea	xx (xx.x%)	xx (xx.x%)	xx (xx.x%)	
Other substance	xx (xx.x%)	xx (xx.x%)	xx (xx.x%)	
Refuse to answer	xx (xx.x%)	xx (xx.x%)	xx (xx.x%)	
Missing	XX	XX	XX	
Correctly Guessed Medication (Subjects that guessed a medicatio	n)			0.xxx
Yes	xx (xx.x%)	xx (xx.x%)	xx (xx.x%)	U.AAA
No	xx (xx.x%)	xx (xx.x%)	xx (xx.x%)	
	An (An,n/o)	Mit (Mil. M/V)	M (MA,N/0)	
Why did you answer above?				0.xxx
Had side effects	xx (xx.x%)	xx (xx.x%)	xx (xx.x%)	
Had no side effects	xx (xx.x%)	xx (xx.x%)	xx (xx.x%)	
Staff treated me different	xx (xx.x%)	xx (xx.x%)	xx (xx.x%)	
No improvement	xx (xx.x%)	xx (xx.x%)	xx (xx.x%)	
Had improvement	xx (xx.x%)	xx (xx.x%)	xx (xx.x%)	
Had a hunch	xx (xx.x%)	xx (xx.x%)	xx (xx.x%)	
I just felt different	xx (xx.x%)	xx (xx.x%)	xx (xx.x%)	
Other	xx (xx.x%)	xx (xx.x%)	xx (xx.x%)	
Refuse to answer	xx (xx.x%)	xx (xx.x%)	xx (xx.x%)	
Missing	XX	XX	XX	
Do you feel the medication helped you to reduce drinking?	(0()	(0()	(0/)	0.xxx
Very Much	xx (xx.x%)	xx (xx.x%)	xx (xx.x%)	
Much	xx (xx.x%)	xx (xx.x%)	xx (xx.x%)	
Moderately	xx (xx.x%)	xx (xx.x%)	xx (xx.x%)	
A little	xx (xx.x%)	xx (xx.x%)	xx (xx.x%)	
Not at all	xx (xx.x%)	xx (xx.x%)	xx (xx.x%)	
Refuse to answer	xx (xx.x%)	xx (xx.x%)	xx (xx.x%)	
Missing	XX	XX	XX	

	Placebo	Oxytocin	Total	
Question	(N=xx)	(N=xx)	(N=xxx)	p-value ¹
How would you describe your experience taking the medication?	?	, ,		0.xxx
Experienced no unwanted side effects and benefited	xx (xx.x%)	xx (xx.x%)	xx (xx.x%)	
Experienced some unwanted side effects but benefited	xx (xx.x%)	xx (xx.x%)	xx (xx.x%)	
Experienced a lot unwanted side effects but benefited	xx (xx.x%)	xx (xx.x%)	xx (xx.x%)	
Experienced no unwanted side effects but did not benefit	xx (xx.x%)	xx (xx.x%)	xx (xx.x%)	
Experienced some unwanted side effects and did not benefit	xx (xx.x%)	xx (xx.x%)	xx (xx.x%)	
Experienced a lot of unwanted side effects and did not benefit	xx (xx.x%)	xx (xx.x%)	xx (xx.x%)	
Refuse to answer	xx (xx.x%)	xx (xx.x%)	xx (xx.x%)	
Missing	XX	XX	XX	
If a friend were in need of help for a drinking problem, would yo	u recommend tak	ing the medication to	him/her?	0.xxx
Yes, definitely	xx (xx.x%)	xx (xx.x%)	xx (xx.x%)	U.AAA
Yes, generally	xx (xx.x%)	xx (xx.x%)	xx (xx.x%)	
Neither yes nor no	xx (xx.x%)	xx (xx.x%)	xx (xx.x%)	
No, not really	xx (xx.x%)	xx (xx.x%)	xx (xx.x%)	
No, definitely not	xx (xx.x%)	xx (xx.x%)	xx (xx.x%)	
Refuse to answer	xx (xx.x%)	xx (xx.x%)	xx (xx.x%)	
Missing	XX	Xx	XX	

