f you were to need treatment in the future, would you choose to				0.xxx
Definitely yes	xx (xx.x%)	xx (xx.x%)	xx (xx.x%)	
Generally yes	xx (xx.x%)	xx(xx.x%)	xx (xx.x%)	
Neither yes or no	xx (xx.x%)	xx (xx.x%)	xx (xx.x%)	
No, not really	xx (xx.x%)	xx(xx.x%)	xx (xx.x%)	
Definitely not	xx (xx.x%)	xx(xx.x%)	xx (xx.x%)	
Refuse to answer	xx (xx.x%)	xx(xx.x%)	xx (xx.x%)	
Missing	XX	Xx	XX	
How much do you think of yourself as wanting to please other po	 	er)?		0.xxx
More than average	xx (xx.x%)	xx (xx.x%)	xx (xx.x%)	0.7272
Average	xx (xx.x%)	xx (xx.x%)	xx (xx.x%)	
Less than average	xx (xx.x%)	xx (xx.x%)	xx (xx.x%)	
Refuse to answer	xx (xx.x%)	xx (xx.x%)	xx (xx.x%)	
Missing	XX	Xx	XX	
0		.1 ****1	1 1 1 1 1 1 1 1 1 1 1 1 1 1 1 1 1 1 1 1	

¹p-value from t-test for continuous variables (t) – skewed continuous data uses the Wilcoxon rank-sum test (w) - chi-square test for categorical variables (c).

Table 9: Research Participation by Treatment Group and Week

		Placebo (N=x	x)		Oxytocin (N=xx)		
Study Week ²	n	Cumulative n	Cumulative %	n	Cumulative n	Cumulative %	p-value ¹
Week 1	XX	XX	xx.x%	XX	XX	XX.X%	0.xxx
Week 2	XX	XX	xx.x%	XX	XX	xx.x%	0.xxx
Week 3	XX	XX	XX.X%	XX	XX	XX.X%	0.xxx
Week 4	XX	XX	XX.X%	XX	XX	XX.X%	0.xxx
Week 5	XX	XX	xx.x%	XX	XX	XX.X%	0.xxx
Week 6	XX	XX	xx.x%	XX	XX	XX.X%	0.xxx
Week 7	XX	XX	XX.X%	XX	XX	XX.X%	0.xxx
Week 8	XX	XX	XX.X%	XX	XX	XX.X%	0.xxx
Week 9	XX	XX	XX.X%	XX	XX	XX.X%	0.xxx
Week 10	XX	XX	XX.X%	XX	XX	XX.X%	0.xxx
Week 11	XX	XX	xx.x%	XX	XX	XX.X%	0.xxx
Week 12	XX	XX	xx.x%	XX	XX	XX.X%	0.xxx
Week 13	XX	XX	XX.X%	XX	XX	XX.X%	0.xxx

Fisher's exact test

Numbers and percentages are based on subjects that participated through a given week

Table 10: Number and Percent of Subjects with Drinking Data Provided by the Brief Drinking Questionnaire instead of the TLFB

	J	Placebo	Ox	ytocin	
Study Week	n	%	n	%	p-value ¹
Week 3	XX	xx.x%	XX	xx.x%	0.xxx
Week 4	XX	xx.x%	XX	xx.x%	0.xxx
Week 5	XX	xx.x%	XX	xx.x%	0.xxx
Week 6	XX	xx.x%	XX	xx.x%	0.xxx
Week 7	XX	xx.x%	XX	xx.x%	0.xxx
Week 8	XX	xx.x%	XX	xx.x%	0.xxx
Week 9	XX	xx.x%	XX	xx.x%	0.xxx
Week 10	XX	xx.x%	XX	xx.x%	0.xxx
Week 11	XX	xx.x%	XX	xx.x%	0.xxx
Week 12	XX	xx.x%	XX	xx.x%	0.xxx
Overall	XX	xx.x%	XX	xx.x%	0.xxx

¹Fisher's exact test

Note only rows with values above 0 will be presented

Table 11: Demographic Characteristics

	Placebo	Oxytocin	Total	
Characteristic	(N=xx)	(N=xx)	(N=xxx)	p-value ¹
Age (years)		`	, ,	0.xxx
N	XX	XX	XX	
Mean (SD)	xx.x (xx.xx)	xx.x (xx.xx)	xx.x (xx.xx)	
Median	xx	XX	XX	

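### The between-arm p-value on the correct-guess row of SAP Table 8 does not test the blind, and it can contradict the valid guess-by-arm p-value printed just above it

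*SAP*

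**What the plan says.** The exit interview at the final visit asks subjects which treatment they think they received (Protocol 7.10 and 10.14). SAP 12.1.1, Table 8 reports it in two rows that bear on the blind, each with its own p-value cell:

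- **Guess by arm.** "What medication do you believe you were taking" is tabulated by arm over six answers: placebo, active, both, no idea, other substance, refuse.
- **Correct guess by arm.** "Correctly Guessed Medication (Subjects that guessed a" medication is tabulated yes/no by arm, with a Total column, among those who named a treatment.

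The table footnote assigns a "chi-square test for categorical variables (c"). SAP 9.1 adds "Statistical tests will be two-tailed at a 0.05 Type I error rate". Section 9 of the SAP does not mention the exit interview, name a blinding assessment, or say how either p-value should be read. Protocol 7.6.2 expects the blind to hold, since experience with the spray "has not indicated that any differences would be noticed between formulations".

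**The concern.** The primary endpoint is self-reported drinking by Timeline Followback, so expectancy is an obvious rival explanation for any difference between arms. Readers will look to the exit interview to judge it. A row labelled as correct guesses, with a p-value beside it, is where many will look first.

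Comparing percent correct between arms is the wrong contrast. An intact blind means that the share guessing active is the same in both arms. If that share is not one half, percent correct then differs between arms even though nobody has been unblinded. If both arms are unblinded to the same degree, percent correct is equal and the test shows nothing. The row can therefore signal a problem when the blind held and show none when it failed.

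**Working it through.** **Inputs.** Allocation is an "approximate 1:1 ratio (targeting 50 subjects per group"). SAP 7.0 starts "With an intake sample of 100 subjects (50 subjects per arm) and 12% attrition", which gives 50 × (1 − 0.12) = 44 per arm, matching its own figure ("it is projected that the sample size for primary endpoint analyses will be 88 (44 subjects per arm")). Neither document states a figure for blinding. The number of guessers (20, 30, 40 or 44 per arm) and the guess shares are assumptions. Taking 44 supposes that every analysed subject names a treatment.

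**What each row tests.** Let a_O and a_P be the shares guessing active on oxytocin and on placebo.

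- Guess by arm compares a_O with a_P. An intact blind means a_O = a_P, so this is the right null hypothesis.
- Percent correct is a_O on oxytocin and 1 − a_P on placebo. Comparing them tests a_O + a_P = 1, that is, whether the active share averaged over the arms is 50%.

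**Formula.** With n guessers per arm and a 2×2 table of k versus n − k, the uncorrected chi-square reduces to 2(2k − n)²/n on 1 df.

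**Intact blind, k of n guessing active in each arm.** The correct-guess row compares k/n with (n − k)/n:

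| n per arm | k | chi-square | p, correct-guess row | p, guess by arm |
|---|---|---|---|---|
| 44 | 26 (59%) | 2·8²/44 = 2.91 | 0.088 | 1.0 |
| 44 | 27 (61%) | 2·10²/44 = 4.55 | 0.033 | 1.0 |
| 44 | 31 (70%) | 2·18²/44 = 14.73 | 0.0001 | 1.0 |
| 30 | 18 (60%) | 2·6²/30 = 2.40 | 0.12 | 1.0 |
| 30 | 21 (70%) | 2·12²/30 = 9.60 | 0.002 | 1.0 |
| 20 | 13 (65%) | 2·6²/20 = 3.60 | 0.058 | 1.0 |
| 20 | 14 (70%) | 2·8²/20 = 6.40 | 0.011 | 1.0 |

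The result is the same if the lean is towards placebo. Fisher's exact test at 31/44 gives 0.0002. The threshold of 27/44 is for the uncorrected test. With a continuity correction, 27/44 gives 88(440 − 44)²/44⁴ = 3.68, p = 0.055, and 28/44 gives 88(528 − 44)²/44⁴ = 5.50, p = 0.019.

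**Chance of p < 0.05 on this row under an intact blind.** Let f be the true share guessing active. The normal approximation is Φ{(|2f − 1| − 1.96√(0.5/n)) / √(2f(1 − f)/n)}. With n = 44 it gives 0.47, 0.82 and 0.98 at f = 60%, 65% and 70%. With n = 30 it gives 0.34, 0.65 and 0.89. A valid test would stay near 0.05.

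**Blind broken equally, k of n correct in each arm.** The correct-guess row gives p = 1.0 at any k. Guess by arm gives chi-square 14.73, p = 0.0001 at 31/44, and 2·32²/40 = 51.2, p = 8 × 10⁻¹³ at 36/40.

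**Blind broken in one arm only.** Take 35/44 correct on oxytocin and 22/44 on placebo. The chi-square is 88(35·22 − 9·22)²/(44·44·57·31) = 8.42, p = 0.004. With 22/44 correct on placebo, 22/44 there also guessed active, so guess by arm is the same table and gives the same p.

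**Six-category row.** With 30 guessers and 14 other answers per arm, and 24/30 correct in each arm, the chi-square is 2·18²/30 = 21.6. On 5 df p = 0.0006. Restricted to active versus placebo (1 df) p = 3 × 10⁻⁶. Under an intact blind with 70% guessing active, the six-category p is 1.0.

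**The case against.** The best defence is that the valid comparison sits directly above the faulty one, with its own p-value. The table also prints counts and a Total column. In the intact example Total reads (31 + 13)/88 = 50% correct, which is chance. In the 36/40 example it reads 90%. Listing 23 gives every individual answer. An attentive reader would not be misled, and no text in the SAP makes the correct-guess p-value the verdict on the blind: SAP 9.1 reserves its language of significance for the primary and secondary endpoints. All of this stands, and it limits the severity.

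Three stronger readings are tempting, and the documents or the arithmetic do not support them:

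- *That the blind has no valid check.* It has one, in the guess-by-arm row.
- *That the correct-guess p-value runs opposite to the truth.* It does not. When only one arm is unblinded it can detect this, as the p = 0.004 example shows. It is uninformative about unblinding that is equal in both arms, and it responds to lopsided guessing.
- *That any majority guessing active makes it significant.* It does not: 26/44, 18/30 and 13/20 all miss 0.05.

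The background also makes the broken-blind example unlikely. Protocol 4.1.8 cites a review in which participants could not tell which spray they had received. That leaves the false alarm under an intact blind as the more relevant risk.

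The defence does not justify keeping the cell. A printed test that needs its neighbours to correct it adds nothing, and the SAP gives no rule for choosing when the two disagree.

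**Conclusion.** The point holds as a minor fault in one table shell. Among guessers, the between-arm p-value on correct guesses tests whether guesses average 50% active. That is not a test of the blind. With 44 guessers per arm and an intact blind, it is significant by the uncorrected chi-square once 27 or more in each arm guess active (p ≤ 0.033; p = 0.0001 at 31/44). It is 1.0 whenever both arms are correct at the same rate, however high. Table 8 can thus show p = 1.0 and p = 0.0001 side by side for the same data, and the SAP does not say which governs.

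The algebra does not depend on any assumption. The sizes rest on assumed guess shares and numbers of guessers, which the documents do not supply. No efficacy or safety estimate is affected.

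**What to change.** 1. In Table 8, delete the p-value from the correct-guess row. Keep the counts and add percent correct with a 95% CI for each arm. A blinding index per arm is optional.
2. Add one sentence to SAP section 9 naming guess by arm, restricted to subjects who answered active or placebo, as the assessment of the blind, and put its p-value in the table.
3. Keep the full six-category row as description, so that no-idea and other answers stay visible without entering the test.

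The cost is one shell edit and one sentence. The exit interview already collects everything needed, and the changes can be made before unblinding.

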#### 10.14. Exit Interview

At the final in-clinic visit (or by phone if the subject withdraws early), the subject will complete a questionnaire for his/her impression of whether he/she was receiving active drug or placebo, if they felt that the medication helped drinking, how they would describe their experience taking the medication, if they would recommend it to a friend, if they would take it again if they needed further treatment in the future, and a question about desire to please people. This questionnaire will be completed by the subject electronically and will be both the source and eCRF.

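### Three ordered exit-interview ratings in SAP Table 8 are tested by chi-square, which ignores their order and costs roughly 10–25 points of power against a one-directional shift

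*SAP*

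**What the plan says.** Protocol 10.14 has subjects complete an exit questionnaire that asks, among other things, "if they felt that the medication helped drinking, how they would describe their experience taking the medication", and whether they would recommend it or take it again. SAP 12.1.1, Table 8, lays the answers out by arm with one p-value per question. Three questions have five ordered answers:

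- "Do you feel the medication helped you to reduce drinking": Very Much down to Not at all.
- The item that begins "If a friend were in need of help for a drinking problem": a definite yes down to a definite no.
- The item that asks, if "you were to need treatment in the future, would you choose to" take the medication again: a definite yes down to a definite no.

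Each has a further row, "Refuse to answer", shown as a count and percentage. The Missing row shows a count only.

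Footnote 1 names a t-test for continuous variables and continues: "skewed continuous data uses the Wilcoxon rank-sum test (w) - chi-square test for categorical variables (c"). No trend, rank or ordinal test is named for ordered categories. SAP section 9 has no paragraph on the exit interview, so the footnote is the whole specification.

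**The concern.** The natural question for these items has a direction: did subjects on oxytocin rate the medication better than subjects on placebo? A Pearson chi-square on five levels spends 4 degrees of freedom and gives the same p-value however the columns are shuffled. It therefore has less power against a consistent shift towards favourable answers, and a small p-value does not by itself say which arm was rated better.

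What is at stake is limited to how these three supportive ratings are read. A real shift in perceived benefit or acceptability is more likely to be reported as no difference than it needs to be.

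**Working it through.** **Inputs from the documents.**

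- SAP 9.1: "Statistical tests will be two-tailed at a 0.05 Type I error rate".
- SAP 7.0: "With an intake sample of 100 subjects (50 subjects per arm) and 12% attrition", leaving 44 per arm; d = 0.60 and power 0.80, stated for the primary endpoint.

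Nothing is stated for the exit-interview items, so their response distribution, effect size and refusal rate are assumptions below. So is 44 respondents per arm.

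**1. The plan's own figure.** Noncentrality λ = n·d²/2 = 44 × 0.36 / 2 = 7.92, and √7.92 = 2.814. Power = Φ(2.814 − 1.960) = 0.804, or 0.795 with the noncentral t. The stated 0.80 reproduces.

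**2. Cost of extra degrees of freedom alone.** Hold λ at 7.92 and change only the reference distribution:

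| df | 5% critical value | Power |
|---|---|---|
| 1 | 3.84 | 0.80 |
| 4 (five levels) | 9.49 | 0.60 |
| 5 (six levels) | 11.07 | 0.56 |

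Where the 1-df test has 50–90% power, the loss is 16–22 points at 4 df and 20–26 at 5 df.

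**3. One worked case.** Assume placebo answers are uniform (0.2 each) and oxytocin is shifted by d = 0.60 on a latent normal scale. The cutpoints are ±0.842 and ±0.253, and the oxytocin probabilities become 0.075, 0.122, 0.168, 0.231 and 0.405.

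- Chi-square: λ = n·Σ(p−q)²/(p+q) = 6.61. Power on 4 df is 0.51.
- Wilcoxon: the probability that an oxytocin answer is the more favourable, counting ties as half, is 0.654. With pooled level probabilities m, the tie-corrected standard error is √[(1−Σm³)/12 × 2/44] = 0.060, so z = 0.154/0.060 ≈ 2.56. Power is Φ(2.56 − 1.96) = 0.73.

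**4. Simulation.** 6,000 trials per scenario, 44 per arm, five assumed placebo distributions from uniform to strongly skewed. Monte Carlo error is about 0.6 points per power. Ranges are over the five distributions, with no refusals:

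| Latent d | Chi-square, 5 levels | Wilcoxon | Loss (points) |
|---|---|---|---|
| 0.3 | 0.12–0.15 | 0.22–0.26 | 10–12 |
| 0.4 | 0.21–0.24 | 0.37–0.42 | 17–19 |
| 0.5 | 0.32–0.37 | 0.54–0.59 | 22–23 |
| 0.6 | 0.46–0.52 | 0.70–0.75 | 21–24 |
| 0.8 | 0.72–0.80 | 0.91–0.94 | 13–19 |

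With 5% refusals unrelated to arm, counted as a sixth chi-square level and left out of the Wilcoxon, the loss is 12–13 points at d = 0.3, 19–21 at d = 0.4 and 26–30 at d = 0.6. Taking the five-level runs with and without refusals, and proportional odds ratios of 2 to 3 as well as d of 0.4–0.6, the loss is 16–25 points.

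**5. Checks in the other direction.** With no difference between arms, all tests rejected in 0.040–0.055 of trials, so Type I error is not inflated. With a difference in spread and no net shift, the order reverses: chi-square 0.62–0.66, Wilcoxon 0.06.

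**The case against.** The strongest reply is that nothing planned depends on this table. The exit interview is in no list of primary, secondary, exploratory or safety endpoints, carries no hypothesis, and sits under disposition and compliance. Counts and percentages are printed for every level, so direction is visible whatever the test. That stands, and it limits the point to a small improvement.

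The footnote is also close to boilerplate and does not go item by item. It mentions continuous-data tests although Table 8 has no clearly continuous item. Chi-square remains the natural reading for answers displayed as labelled categories, and no other text competes with it.

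A general-association test can also be defended. Protocol 4.1.6 describes a laboratory study in which oxytocin lowered craving in more anxiously attached subjects and raised it in less anxiously attached ones. Opposed responses are therefore conceivable, and step 5 shows chi-square is far better at detecting them. This is a real trade-off, so the change is not free of any downside.

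A reader might infer more than the documents support:

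- **Refusals are a level of the test.** The percentage on that row fixes the display denominator only. The SAP does not say what enters the chi-square, and Listing 23 shows no refusal option for these items.
- **The loss is one fixed figure.** The d of 0.60 belongs to the primary endpoint, and the loss depends on the assumed shift.
- **A moderate shift would usually be missed only because of chi-square.** At d = 0.6 chi-square has roughly even odds; at d = 0.4 the Wilcoxon test also has only 0.37–0.42 power.
- **These are the only patient ratings of benefit.** The experience item in the same table crosses benefit with side effects.

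**Conclusion.** The point holds as a minor improvement. Footnote 1 places three ordered 5-point ratings under a test that ignores their order, and no reason is given.

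Against a one-directional shift with 44 respondents per arm and two-sided 0.05, the cost is roughly 10–25 points of power: about 10–13 at a latent d of 0.3 and about 15–25 at d of 0.4–0.6. It rises to 26–30 points at d = 0.6 if 5% refusals were a sixth level. These figures rest on assumed response distributions, shifts and refusal rates. They do not apply to a difference in spread alone, where chi-square is the better test. No primary or secondary conclusion is affected.

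**What to change.** Amend footnote 1 of SAP Table 8 along these lines: *For the three ordered ratings (helped reduce drinking, recommend to a friend, choose to take again) the p-value is from the Wilcoxon rank-sum test on the ordered responses. Refusals are reported in the table but left out of the test. Chi-square is used for the unordered items (medication guess, reason for the guess, experience).*

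The Wilcoxon test is already named in that footnote, so the cost is one sentence and a line of code, with no new data. Keep the full counts and percentages, because they are where a difference in spread without a net shift would still be seen. Protocol 11.1 has the SAP completed before database lock and unblinding. If that point has not passed, the change can be prespecified; if it has, it can be disclosed in the final study report, as the same section provides.
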